#### Time-to-event endpoints

The endpoints;

- Time to having a decrease in EASI of at least 50% (EASI 50) between baseline and Week 16.
- Time to having a decrease in EASI of at least 75% (EASI 75) between baseline and Week 16.
- Time to having a decrease in EASI of at least 90% (EASI 90) between baseline and Week 16.
- Time to initiation of TCI or TCS rescue treatment between baseline and Week 16.

will be analysed according to Gray's test, stratified by region and baseline disease severity. Gray's test accounts for the occurrence of the competing risks, permanent discontinuation of IMP and initiation of rescue treatment. Inference will be based on the estimated cumulative incidence of achieving the endpoint derived from the Aalen-Johansen estimator. The

THIS DOCUMENT CONTAINS CONFIDENTIAL INFORMATION AND MUST NOT BE COPIED OR MADE AVAILABLE TO ANY THIRD PARTY WITHOUT THE PRIOR WRITTEN CONSENT OF THE LEO PHARMA GROUP

estimated cumulative incidence functions will be presented by treatment group along with 95% confidence bands.

### 14.3.11 Analysis of patient-reported outcomes

#### Continuous endpoints

The following endpoints;

- Change in Worst Daily Pruritus NRS (weekly average) from baseline to Weeks 1, 2, 4, 8, 12, and 16.
- Change in POEM score from baseline to Week 16.
- Change in DLQI from baseline to Week 16.

will be summarised descriptively at each visit by treatment group and will be analysed using a MMRM model including treatment, visit, interaction between treatment and visit, region and baseline disease severity as factors and adjusting for baseline value for the endpoint of interest as covariate. The model will use an unstructured covariance matrix, Kenward Roger approximation to estimate denominator degrees of freedom. For these endpoints, data collected after permanent discontinuation of IMP or after initiation of rescue treatment will not be included in the analysis but will be ‘treated as missing’. This model assumes that data is missing at random within each treatment group. The estimates will be presented with nominal p-values and 95% CI at each visit.

#### Binary endpoints

The following endpoints;

- Having a decrease in Worst Daily Pruritus NRS (weekly average) of  $\geq 3$  points from baseline at Weeks 1, 2, 4, 8, 12, and 16, assessed separately.
- Having a decrease in Worst Daily Pruritus NRS (weekly average) of  $\geq 4$  points from baseline at Weeks 1, 2, 4, 8, 12, and 16, assessed separately, among subjects with a baseline Worst Daily Pruritus NRS  $\geq 4$  points.

will be summarised descriptively at each visit by treatment group and will be analysed using the same CHM test described in Section [14.3.10](#) for binary endpoints.

THIS DOCUMENT CONTAINS CONFIDENTIAL INFORMATION AND MUST NOT BE COPIED OR MADE AVAILABLE TO ANY THIRD PARTY WITHOUT THE PRIOR WRITTEN CONSENT OF THE LEO PHARMA GROUP

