Main criteria for inclusion	
 
18-64 years old (both included) at screening.
 
Diagnosis of AD [as defined by the AAD Consensus Criteria (1)] that has been present for ≥1 year prior to screening.
 
Subjects who have a recent history (within 6 months before screening) of inadequate response to treatment with topical medication, or for whom topical treatments are otherwise medically inadvisable.
 
EASI score ≥12 at screening and ≥16 at baseline.
 
vIGA-AD score ≥3 at screening and baseline.
 
Body surface area (BSA) of AD involvement ≥10% at screening and baseline.
 
Worst Daily Pruritus NRS (weekly average) of ≥3 points at baseline.
 

Main criteria for exclusion	
 
Treatment with systemic immunosuppressive/immunomodulating medication, immunoglobulin/blood products, or phototherapy within 4 weeks or 5 half-lives prior to randomisation, whichever is longer.
 

	
 
Treatment with biologics within 5 half-lives (if known) or 16 weeks prior to randomisation, whichever is longer.
 
Treatment with TCS, TCI, topical PDE-4 inhibitor, or other topical prescription treatments within 1 week prior to randomisation.
 
Treatment with a live (attenuated) vaccine within 12 weeks prior to randomisation.
 
Clinically significant active chronic or acute infection requiring systemic treatment within 4 weeks prior to randomisation that may compromise the safety of the subject.
 
Skin infection within 1 week prior to randomisation.
 
Presence of hepatitis B or C infection at screening.
 
History of human immunodeficiency virus (HIV) infection or positive HIV serology at screening.
 
Subject has a positive or indeterminate test for tuberculosis at screening.
 
Subject is pregnant or lactating.
 

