## Randomisation (Week 0)

At baseline (Visit 3, Week 0), eligible subjects will be randomised 1:1 to 1 of 2 treatment groups: LEO 138559 or placebo. Randomisation will be stratified by baseline disease severity. One stratum, 'stratum A', will be defined as having EASI <21 and the other stratum, 'stratum B', will be defined as having EASI  $\geq 21$ . IRT will be used to control randomisation and stratification factors.

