*NOTE: The baseline weekly average will be calculated from daily assessments of itch severity during the 7 days immediately preceding randomisation. A minimum of 4 daily itch scores out of the 7 days is required to calculate the baseline average score. For subjects who do not have at least 4 daily itch scores reported during the 7 days immediately preceding the planned randomisation date, randomisation can be postponed until the requirement of 4 daily entries is met, but without exceeding the 28-day maximum duration for screening.*
9. Subject agrees to apply an emollient twice daily (or more frequently, if needed) to AD lesional and non-lesional skin for at least 7 days before baseline.
10. A woman of childbearing potential\* must have a negative serum pregnancy test at screening and a negative urine pregnancy test at baseline.
11. A woman of childbearing potential\* must use a highly effective\*\* form of birth control throughout the trial and at least for 18 weeks after last administration of IMP.

\* A woman of childbearing potential is defined as a female subject aged  $\geq 12$  years old or a younger girl who, at the discretion of the investigator, is deemed to be of reproductive potential. A woman is defined as not being of childbearing potential if she is postmenopausal (at least 12 months with no menses without an alternative medical cause prior to screening), or surgically sterile (hysterectomy, bilateral salpingectomy, or bilateral oophorectomy).

THIS DOCUMENT CONTAINS CONFIDENTIAL INFORMATION AND MUST NOT BE COPIED OR MADE AVAILABLE TO ANY THIRD PARTY WITHOUT THE PRIOR WRITTEN CONSENT OF THE LEO PHARMA GROUP

\*\*A highly effective method of birth control is defined as one which results in a low failure rate (less than 1% per year) such as bilateral tubal occlusion, intrauterine device (IUD), intrauterine hormone-releasing system (IUS), combined (oestrogen- and progestogen-containing) hormonal contraception associated with inhibition of ovulation (oral, intravaginal, transdermal), progestogen-only hormonal contraception associated with inhibition of ovulation (oral, injectable, implantable), sexual abstinence (when this is in line with the preferred and usual life style of the subject and not just being without a current partner), same-sex partner, or vasectomised partner (given that the subject is monogamous).

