### 14.3.10 Analysis of exploratory efficacy endpoints

#### Binary endpoints

The following endpoints;

- Having a decrease in EASI of at least 50% (EASI 50) from baseline to Week 16.
- Having a decrease in EASI of at least 75% (EASI 75) from baseline to Week 16.
- Having a decrease in EASI of at least 90% (EASI 90) from baseline to Week 16.
- Having vIGA-AD of 0 (clear) or 1 (almost clear) at Week 16.

will be analysed using CMH test stratified by region and baseline disease severity. Subjects who received rescue treatment prior to the Week 16 visit or permanently discontinued IMP or have missing data will be considered as non-responders. Additionally, responder rates will be summarised descriptively at each visit by treatment group.

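### The itch-responder tests leave out baseline itch, which costs some precision and lets chance baseline imbalance move the responder difference

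*Combined protocol and SAP*

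**What the plan says.** Section 14.3.11 (Binary endpoints) defines itch response as a fall in the weekly-average Worst Daily Pruritus NRS of at least 3 points, or at least 4 points, at Weeks 1, 2, 4, 8, 12 and 16. Both endpoints are summarised by visit, and each "will be analysed using the same CHM test described in Section" 14.3.10. There, the EASI and vIGA-AD responder endpoints "will be analysed using CMH test stratified by region and baseline disease severity". The non-responder rule is also given there: "Subjects who received rescue treatment prior to the Week 16 visit or permanently discontinued IMP or have missing data will be considered as non-responders".

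Baseline itch appears in three other places:
- **Eligibility.** The synopsis and inclusion criterion 8 in Section 8.2 require a "Worst Daily Pruritus NRS (weekly average) of ≥3 points at baseline". The note to that criterion adds: "The baseline weekly average will be calculated from daily assessments of itch severity during the 7 days immediately preceding randomisation". At least 4 of 7 daily scores are needed, and randomisation can be postponed until they exist.
- **The 4-point endpoint.** It is "assessed separately, among subjects with a baseline Worst Daily Pruritus NRS" of at least 4.
- **The continuous itch endpoint.** The mixed model for change in the same NRS at the same six weeks is fitted "adjusting for baseline value for the endpoint of interest as covariate".

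Baseline itch is not a randomisation factor. Under Section 7.1, "Randomisation will be stratified by baseline disease severity", with strata EASI below 21 and EASI 21 or above. Panel 3 lists the itch endpoints as exploratory, and Section 14.3.7 treats all p-values as nominal.

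**The concern.** EASI 50, 75 and 90 are relative falls. Itch response is an absolute fall on a 0 to 10 scale, so its difficulty depends on where the subject starts. The stratum set is carried over from the EASI and vIGA-AD endpoints and omits the baseline of the score being dichotomised. The mixed model in the same section includes it, and no reason is given for the difference.

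With 26 subjects per arm and no stratification on itch, the arms will differ somewhat in mean baseline NRS by chance. That difference carries into the estimated responder difference. The same baseline values feed all twelve comparisons (six visits, two thresholds), so the shift does not average out over visits and could look like a consistent effect over time. The value that would remove it is already collected for essentially every randomised subject.

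**Working it through.** **The plan's own figure.** No power or responder rate is stated for the itch endpoints. The only sample-size figure (Section 14.1) concerns EASI. With a difference of 22.9 − 7.3 = 15.6 and a root-mean-square SD of 15.70 (from SDs 13 and 18), a t-test with 18 per group has 82.5% power. Then 18/0.70 gives 26 randomised per group. The figure reproduces but does not bear on itch.

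**Step 1: how the target depends on baseline.** Required relative fall = threshold / baseline.
- At least 3 points: 3/3 = 100% at baseline 3; 3/10 = 30% at baseline 10.
- At least 4 points: 4/4 = 100% at baseline 4; 4/10 = 40% at baseline 10.

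This uses only the documents.

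**Step 2: size of the effect.** The documents give no itch distribution, so these inputs are assumptions: baseline NRS mean 7 (SD 1.8) or 6 (SD 2.0), truncated to 3–10; mean proportional itch reduction 25% on placebo and 50% on active, or 25% on both for no effect; between-subject SD of the reduction 0.15 or 0.30; 15% imputed as non-responders; correlation of itch with EASI severity 0.3. In each of 3,000 to 4,000 simulated trials per setting, 52 subjects were randomised 1:1 within EASI strata. A linear model for the responder difference with severity and region was fitted with and without baseline NRS.

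Results with a true effect:

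| Fall | Baseline mean (SD) | SD of reduction | Response, placebo / active | Variance cut | Shift per 1-point imbalance, unadjusted | Adjusted | Power without → with NRS |
|---|---|---|---|---|---|---|---|
| ≥3 | 7 (1.8) | 0.15 | 11% / 51% | 9.2% | 8.7 pp | −0.8 pp | 90.9 → 93.3% |
| ≥3 | 7 (1.8) | 0.30 | 22% / 47% | 2.6% | 6.8 pp | 0.0 pp | 47.8 → 49.0% |
| ≥3 | 6 (2.0) | 0.15 | 8% / 41% | 12.6% | 9.9 pp | 0.5 pp | 84.0 → 88.6% |
| ≥3 | 6 (2.0) | 0.30 | 18% / 41% | 4.8% | 7.0 pp | −0.4 pp | 45.1 → 47.1% |
| ≥4 | 7 (1.8) | 0.15 | 3% / 28% | 7.1% | 7.2 pp | −0.3 pp | 75.2 → 77.6% |
| ≥4 | 7 (1.8) | 0.30 | 12% / 33% | 2.8% | 6.4 pp | 0.0 pp | 41.5 → 43.3% |
| ≥4 | 6 (2.0) | 0.15 | 2% / 21% | 8.4% | 7.2 pp | 0.0 pp | 53.6 → 57.4% |
| ≥4 | 6 (2.0) | 0.30 | 10% / 28% | 4.0% | 6.5 pp | −0.4 pp | 35.7 → 36.9% |

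With no effect, the variance cut was 0.9% to 5.2% and the unadjusted shift 2.8 to 6.2 percentage points. Over all settings this gives a variance cut of about 1% to 13% and a shift of about 3 to 10 points, against about 0 after adjustment. Simulations with somewhat different assumptions gave variance cuts of 3% to 11% and about 3% to 8% under a true effect.

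**Step 3: how large an imbalance to expect.** The SD of the between-arm difference in mean baseline NRS was 0.40 to 0.45 point. A difference of 0.5 point or more arose in 21% to 27% of trials. A one-SD imbalance therefore moves the unadjusted responder difference by about 0.40 × 2.8 = 1.1 to 0.45 × 9.9 = 4.5 percentage points. For scale, one responder in 26 is 1/26 = 3.8 points.

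**Step 4: validity.** With no effect, the planned CMH test rejected in 0.4% to 5.6% of trials, and in 0.5% to 6.4% of those with an imbalance of 0.5 point or more. The upper figures lie within about two simulation standard errors of 5%.

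**The case against.** The strongest case on the other side is that nothing here is an error. Randomisation protects the test, chance imbalance in an unstratified covariate is part of the randomisation distribution, and the CMH test holds its level. The endpoints are exploratory, with nominal p-values and no power claim. A baseline-adjusted model of the same score is already planned at the same weeks, and Sections 14.3.1 and 14.3.13 leave room to add analyses before unblinding. All of this stands, and it makes the point minor. It does not remove the point: the mixed model estimates a mean change and cannot supply an adjusted responder difference.

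A reader might also infer more than the documents support:
- **That low-baseline subjects cannot respond.** The entry floor of 3 and the restriction of the 4-point endpoint to baseline 4 or more make the fall possible for everyone analysed. Baseline changes how hard it is; the simulated correlation of baseline with response was only 0.20 to 0.36.
- **That baseline itch belongs in the CMH strata.** Swapping region for an itch category does raise power, but mostly because sparse region strata disappear. In one two-region setting, power was 0.748 as planned, 0.766 with severity alone and 0.767 with severity and itch. Adding an itch split to the planned strata lowers power, for example from 47.7% to 45.0%.

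**Conclusion.** The point holds as a minor, low-cost improvement. The planned itch-responder test is valid but omits a baseline value that affects how easily response is reached and that the plan uses for the continuous version of the same score. Under the assumptions in Step 2, including it as a covariate cuts the variance of the responder difference by about 1% to 13%, adds about 1 to 5 points of power against the same model without it, and removes a shift of roughly 3 to 10 percentage points per 1-point baseline imbalance.

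Only the dependence of the target on baseline (Step 1) follows from the documents alone. The magnitudes rest on assumed itch distributions and on a linear model rather than the logistic form suggested below. The documents do not support calling the test biased, or saying that baseline decides who can respond.

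**What to change.** Keep the CMH test and its strata for both itch-responder endpoints; do not replace or further split the strata. In the SAP, before unblinding, pre-specify for these two endpoints a covariate-adjusted difference in proportions with 95% CI. The model should contain treatment, region, baseline disease severity and the baseline NRS weekly average as a continuous covariate, for example a logistic model standardised to a risk difference. The non-responder rule stays as planned. Reference 59 in Section 15 is, by its title, a paper on this kind of method, although the protocol text does not appear to cite it. Correct CHM to CMH in the same edit.

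The cost is a short addition to the SAP and one extra analysis; no new data are needed. The model may be unstable at early visits with few responders, so the SAP should say that the CMH result then stands alone.

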## Time-to-event endpoints

The endpoints;

- Time to reduction of Worst Daily Pruritus NRS (weekly average) of  $\geq 3$  points between baseline and Week 16.
- Time to reduction of Worst Daily Pruritus NRS (weekly average) of  $\geq 4$  points between baseline and Week 16 among subjects with a baseline Worst Daily Pruritus NRS  $\geq 4$  points.

will be summarised descriptively at each visit by treatment group and will be analysed using the same analysis method described in Section [14.3.10](#) for time-to-event endpoints.

## 14.3.12 Analysis of pharmacodynamics

For the following endpoints;

- Change in expression of AD disease biomarkers in serum from baseline to Week 16.
- Change in expression of AD disease biomarkers in skin from baseline to Week 16.

explorative analyses will be performed for the total population as well as by baseline disease severity.

A summary of the results will be included in the CTR if the results are available in time for this. The full set of biomarker results will be reported in an addendum to the CTR.

## 14.3.13 Exploratory analyses

Descriptive statistics of BSA score (absolute and change from baseline) will be summarised at each visit by treatment group. Additional exploratory analyses will be described in the SAP and will be performed if deemed necessary.

## 14.3.14 Analysis of safety

The analysis of safety will be based on the safety analysis set.

### 14.3.14.1 Adverse events

AEs will be coded during the course of the trial according to the MedDRA. AEs will be presented by preferred term and primary SOC.

Treatment-emergent AEs will be summarised; however, all AEs recorded during the course of the trial will be included in subject data listings. Treatment-emergent and non-treatment-emergent AEs will be listed separately. An event will be considered treatment-emergent if

THIS DOCUMENT CONTAINS CONFIDENTIAL INFORMATION AND MUST NOT BE COPIED OR MADE AVAILABLE TO ANY THIRD PARTY WITHOUT THE PRIOR WRITTEN CONSENT OF THE LEO PHARMA GROUP

started after the first dose of IMP or if started before the first dose of IMP and worsened in severity after first dose of IMP. An event will not be considered treatment-emergent if starting 18 weeks after the last dose of IMP. The tabulations described in the following will only include the treatment-emergent events. In each of the tabulations, AEs are defined by MedDRA preferred terms within primary SOC.

AEs will be summarised in terms of the number of subjects with at least 1 event, the percentage of subjects with at least 1 event, the number of events, and the event rate per 100 patient years of observation time.

Related AEs are defined as AEs for which the investigator has not described the causal relationship to IMP as 'not related'.

An overall summary of the number of events and the number (percentage) of subjects with any treatment-emergent AEs, deaths, SAEs, AESIs, permanent discontinuations from IMP, and/or withdrawals from the trial due to AEs, treatment-related AEs, mild and moderate AEs, and severe AEs will be presented.

Tabulations by SOC and preferred term will be presented for all AEs, SAEs, related AEs, AESIs, and AEs leading to withdrawal from trial and/or permanent discontinuation of IMP. In addition, all AEs will be presented by severity and causal relationship to IMP, respectively.

The number of AEs and number of subjects with each type of AEs will be tabulated by treatment group from baseline to Week 16, from baseline to Week 32, and from Week 17 to Week 32.

SAEs will be evaluated separately and a narrative will be given. AESIs will be tabulated and listed by treatment group, no narratives will be given except if these are serious.

AEs leading to withdrawal from trial and/or permanent discontinuation of IMP will be tabulated and listed. The detailed listing will provide an overview of the individual cases and include the age and sex of the subject, treatment received at the time of AE onset, the AE preferred and reported terms, causality and severity of the AE, the action taken with the IMP, AE outcome, start and stop date of AE, duration of AE, and number of days since first and last IMP administration. No narratives will be given.

THIS DOCUMENT CONTAINS CONFIDENTIAL INFORMATION AND MUST NOT BE COPIED OR MADE AVAILABLE TO ANY THIRD PARTY WITHOUT THE PRIOR WRITTEN CONSENT OF THE LEO PHARMA GROUP

#### **14.3.14.2 Vital signs and physical examination**

The change in vital signs (blood pressure, pulse, and body temperature) from baseline to each relevant visit will be summarised by treatment group as mean, standard deviation (SD), median, minimum and maximum values for the safety analysis set.

Subjects with abnormal, clinically significant physical findings will be listed. Furthermore, a shift table for physical findings showing the change from baseline to Week 16 in clinical assessments (normal; abnormal, not clinically significant; abnormal, clinically significant) will be performed.

#### **14.3.14.3 ECG**

The change in ECG from baseline to each visit will be summarised by treatment group as mean, SD, median, minimum and maximum values for the safety analysis set.

Subjects with abnormal, clinically significant ECG will be listed. Furthermore, a shift table for ECG showing the change from baseline to Week 16 in clinical assessments (normal; abnormal, not clinically significant; abnormal, clinically significant) will be performed.

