## 10 Discontinuation and withdrawal

### 10.1 General principles

A subject may withdraw from the trial (prior to first dose or during the treatment period) or permanently discontinue trial treatment at any time if the subject, the investigator, or LEO Pharma considers that it is not in the subject's best interest to continue.

A subject who withdraws from the trial is a subject who stops treatment with the IMP and all further protocol defined trial activities. A subject who permanently discontinues IMP is a subject who, although they stop treatment with the IMP, agree to their follow-up as described in Section 10.3. Early termination assessments to be conducted for both events are described in Section 10.3.

Subjects who withdraw from the trial and subjects who permanently discontinue IMP will not be replaced.

If a subject withdraws from the trial, they may request destruction of any samples taken and not tested. The investigator must document this in the subject's medical record and inform LEO Pharma.

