### **Withdrawal from trial**

Subjects who withdraw/are withdrawn from the trial prior to first dose of IMP (randomisation) will be considered screening failures.

Subjects who withdraw from the trial for any reason should attend an early termination visit as soon as possible after last administration of IMP. Assessments/procedures to be conducted at this visit are listed in the schedule of trial procedures (Section 4). If the subject agrees, the investigator will review any AEs which will be followed up according to Section 13.7.

Details on data to be recorded in the eCRF for subjects who withdraw from the trial can be found in Section 11.7.

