### 11.4.4 ECG

ECGs must be measured according to the schedule of trial procedures in (Section 4). At an unscheduled visit, it will be at the discretion of the investigator if an ECG should be measured.

At each visit, the individual measurements as well as the average of 3 consecutive 12-lead resting digital ECG measurements will be recorded after the subject has been in supine position for at least 5 minutes.

A pre-evaluation of the ECGs will be performed by the investigator to evaluate immediate subject safety. At a minimum, the date of ECG pre-evaluation will be recorded in the source documents. In case of a suspected abnormal ECG, the investigator must take appropriate action, at their discretion.

The ECG data will be transferred to a central ECG service company for central evaluation. A cardiologist at the ECG service company will analyse and interpret the ECG data. The ECG service company will provide ECG evaluation reports to the trial sites.

The investigator must evaluate all abnormal ECG results ('clinically significant' or 'not clinically significant') and sign and date when the evaluation is performed. The investigator has the final decision on the clinical significance of ECG abnormalities.

If a result is abnormal at the screening or baseline visit and considered by the investigator to be clinically significant, it will be up to the investigator's discretion to decide if the subject should be enrolled into the trial (respecting exclusion criteria no. 18 and 27). If a subject with an abnormal and clinically significant ECG result is enrolled, the investigator should provide a justification in the medical record.

During the trial if a subject presents with a clinically significant abnormal ECG or a clinically significant abnormal change in ECG from baseline, the ECG should be repeated. If the ECG or change in ECG is confirmed clinically significantly abnormal, the subject must permanently discontinue IMP, and be withdrawn from the trial. In such case, the subject

THIS DOCUMENT CONTAINS CONFIDENTIAL INFORMATION AND MUST NOT BE COPIED OR MADE AVAILABLE TO ANY THIRD PARTY WITHOUT THE PRIOR WRITTEN CONSENT OF THE LEO PHARMA GROUP

should be monitored until the subject's ECG returns to a state similar to that of screening/baseline at the discretion of the investigator.

The collection and transmission of ECG data will be described in a separate ECG manual.

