## 14.3 Statistical analysis

### 14.3.1 General principles

All significance tests will be two-sided using the 5% significance level. All confidence intervals will be presented with 95% degree of confidence, unless otherwise specified. Efficacy analyses will be based on the FAS, and safety analyses will be based on the safety analysis set. PK analysis will be based on the PK analysis set.

If not mentioned otherwise, endpoints will be summarised descriptively at each visit by treatment. For endpoints evaluated over time, plots will be made to explore the trajectories with time.

An observed cases approach will be used for tabulations of data by visit (that is, involving only those subjects who attended each specific visit). For categorical endpoints, the number of subjects not attending each specific visit will also be provided.

Categorical data will be summarised by treatment group, using the number and percentage of subjects in each category. Continuous data will be summarised using the mean, median, standard deviation (SD), 1st quartile, 3rd quartile, minimum, and maximum values.

Additionally, geometric mean and coefficient of variation (CV) will be provided for the PK endpoint.

In general, for endpoints evaluated as change from baseline and/or where a baseline adjustment is applied, baseline is defined as assessments conducted at the randomisation visit (Visit 3), if not otherwise stated. If the information is not available at the randomisation visit but at the (re)screening visit (Visit 1) then this will be used instead.

All the analyses specified in the protocol will be reviewed in relation to the blinded data actually obtained, and the statistical analysis plan will be finalised before breaking the randomisation code.

Any changes from the statistical analyses planned in this clinical trial protocol will be described and justified in a protocol amendment, the statistical analysis plan, and/or in the CTR, dependent on the type of change.

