#### **14.3.14.4 Clinical laboratory evaluation**

The change in each of the laboratory parameters from baseline to each visit will be summarised by treatment group as mean, SD, median, minimum and maximum values for the safety analysis set.

Laboratory parameters will be classified as ‘low’, ‘normal’, or ‘high’, depending on whether the value is below, within, or above the reference range, respectively. A shift table will be produced showing the categories at baseline against those at the end of treatment. Subjects with laboratory parameters outside the reference range will be listed.

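### The ECG, physical-finding and laboratory shift tables use one late time point, so earlier category shifts are not counted by arm and a subject withdrawn for a confirmed abnormal ECG before Week 16 drops out of the ECG shift table

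*Combined protocol and SAP*

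**What the plan says.** Section 14.3.14 plans three shift tables.

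- **ECG (14.3.14.3):** "a shift table for ECG showing the change from baseline to Week 16 in clinical assessments", with the categories normal, abnormal but not clinically significant, and abnormal and clinically significant.
- **Physical examination (14.3.14.2):** "a shift table for physical findings showing the change from baseline to Week 16 in clinical assessments", with the same three categories.
- **Laboratory (14.3.14.4):** "A shift table will be produced showing the categories at baseline against those at the end of treatment", with the categories low, normal and high.

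None of these sections plans a shift to the worst post-baseline value, to the last on-treatment value, or to each visit. Section 14.3.1 adds that "An observed cases approach will be used for tabulations of data by visit".

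Section 11.4.4 sets the consequence of an abnormal ECG during the trial: "If the ECG or change in ECG is confirmed clinically significantly abnormal, the subject must permanently discontinue IMP, and be withdrawn from the trial". Section 10.1 defines withdrawal: "A subject who withdraws from the trial is a subject who stops treatment with the IMP and all further protocol defined trial activities". Section 10.3 leaves one further visit: "Subjects who withdraw from the trial for any reason should attend an early termination visit as soon as possible after last administration of IMP". Panel 2 marks ECG, physical examination and laboratory tests for that visit, but nothing in Section 14 assigns its results to Week 16.

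**The concern.** A shift table shows by arm how many subjects moved from one category to a worse one. With a single late time point it misses a change that appeared and resolved earlier. For ECG there is a second problem: the exclusion depends on the outcome being tabulated. A confirmed clinically significant ECG before Week 16 leads to withdrawal, and withdrawal removes the subject from the only time point the table uses. The worst category at Week 16 can therefore contain nobody who met that rule earlier.

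Comparing safety with placebo is the trial's secondary objective, and Section 12.2 gives a specific reason for collecting ECGs, namely possible indirect cardiac effects of large proteins. With 26 subjects per arm, one subject is 1/26 = 3.8%, so a missing subject changes the descriptive picture. What is at stake is the completeness of descriptive safety reporting, not a test or an endpoint.

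**Working it through.** The shift tables carry no planned figure of their own, so the check is mainly a comparison of sections.

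**1. Visits inside and outside the tables (Panel 2).**

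| Assessment | Post-baseline visits up to Week 16 | In the shift table | Outside |
|---|---|---|---|
| ECG | Weeks 4, 8, 12, 16 | Week 16 | 3 of 4 |
| Physical examination | Weeks 4, 8, 12, 16 | Week 16 | 3 of 4 |
| Chemistry and haematology | Weeks 2, 4, 8, 12, 16 | Week 16, if that is what end of treatment means | 4 of 5 |

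The condition in the last row matters. Panel 2 labels the Week 16 visit as end of treatment, but 14.3.14.4 does not say Week 16. By contrast, Section 11.6.4 on tape strips names the early IMP termination visit beside the end-of-treatment visit. For laboratory tests, an early-termination value might or might not enter the table.

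**2. A subject with a confirmed clinically significant ECG at, say, Week 8.** Under 11.4.4, "the subject must permanently discontinue IMP, and be withdrawn from the trial". Under 10.1, protocol activities then end. Under 10.3 there is an early termination visit. There is no Week 16 ECG, by-visit tabulation uses observed cases, and no rule maps the early-termination ECG to Week 16. The subject has no entry in the ECG shift table, nor in the physical-finding table, which uses the same time point.

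**3. Where that subject does appear.** Section 11.4.4 requires a new clinically significant ECG finding to be reported as an adverse event. Section 14.3.14.1 tabulates adverse events by treatment group from baseline to Week 16, with numbers and percentages of subjects. It also tabulates events leading to withdrawal or IMP discontinuation. Section 14.3.14.3 lists subjects with a clinically significant ECG without restriction to a visit.

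As an illustration, assume all 26 subjects in the LEO 138559 arm are exposed and 2 of them (2/26 = 7.7%) have such an ECG at Week 4 or 8. The shift table would show 0 of at most 26 − 2 = 24, while the adverse event tables would count 2 of 26.

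**4. What appears in no by-arm categorical table.**

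- ECG and physical findings that moved from normal to abnormal, not clinically significant, at Weeks 4 to 12 and then resolved. The listings cover clinically significant findings only, and these changes need not be adverse events.
- Laboratory values that left the reference range at Weeks 2 to 12 and then returned, unless judged clinically significant. They are listed, but not counted by arm.

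The general rule in 14.3.1 that endpoints are summarised at each visit does not fill this gap, because ECG, physical-examination and laboratory categories are not among the endpoints in Panel 3.

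**5. How many subjects could lack a Week 16 value.** Section 14.1 inflates 18 per group for 30% attrition: 18 / (1 − 0.30) = 25.7, rounded up to 26, which reproduces the plan. Applied to Week 16, 26 × 0.30 = 7.8, or about 8 per arm without a value. This is an upper bound. The 30% is stated as a maximum, and subjects who stop IMP but stay in the trial are asked back at Week 16 (Panel 2, footnote c; Section 10.3).

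Those returning subjects raise a smaller point. Someone who stopped IMP at Week 4 would be tabulated with a value taken 16 − 4 = 12 weeks later, off treatment.

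**The case against.** The strongest reply is that the safety report does not depend on these tables. New clinically significant ECG, physical and laboratory findings must be reported as adverse events (11.4.2, 11.4.4, 11.4.5.2), which are tabulated by arm with counts and percentages, and again where they lead to discontinuation or withdrawal. ECG and laboratory changes are also summarised by arm at each visit with minimum and maximum, and with 52 subjects the listings can be read in full. Baseline-to-endpoint and baseline-to-worst are both accepted descriptive displays. Finally, 14.3.1 says a statistical analysis plan will be finalised before the code is broken, and it may add such a table. The statistical text available here is protocol Section 14.

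Most of this stands, and it rules out several stronger readings that a reader might infer:

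- **That a subject stopped for an abnormal ECG vanishes from the report.** The adverse event tables and the ECG listing include that subject. The exclusion concerns the Week 16 shift tables.
- **That safety reporting as a whole is biased towards showing no signal.** Clinically significant events are counted by arm elsewhere.
- **That the laboratory table must exclude early stoppers.** Its time point is undefined for them, and tests are scheduled at early termination.
- **That about 8 of 26 per arm will have no Week 16 value, or that the tables hold only subjects who completed treatment.** Subjects who stop IMP are invited back for that visit.

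The reply does not supply the missing counts. By-visit means and ranges do not show how many subjects changed category, and listings give no by-arm denominators.

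**Conclusion.** The point holds as a limited gap in descriptive safety reporting. The ECG and physical-finding shift tables omit 3 of 4 visits up to Week 16. The laboratory table omits 4 of 5 draws if end of treatment means Week 16, and is ambiguous otherwise. A subject withdrawn before Week 16 for a confirmed clinically significant ECG cannot appear in the ECG shift table, because no rule brings early-termination data into Week 16. The practical loss is a by-arm count of earlier or transient shifts, chiefly ECG and physical findings judged not clinically significant and laboratory values that later normalise. How many subjects this would affect cannot be derived from the documents. No primary or secondary endpoint analysis changes. The conclusion rests on Section 14 as written; a later analysis plan that adds a worst-value shift would close the point.

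**What to change.** In 14.3.14.2 to 14.3.14.4, or in the analysis plan before unblinding:

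1. Add a shift from baseline to the worst post-baseline category up to Week 16, including early-termination and unscheduled assessments. For laboratory tests, show worst low and worst high separately.
2. Use as denominator the safety-set subjects with a baseline and at least one post-baseline value, by arm.
3. Keep the Week 16 shift alongside.
4. Define end of treatment for early stoppers: state whether the early-termination value or the nominal Week 16 value is used.

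The plan already takes an any-time view for anti-drug antibodies (14.3.14.5 classifies each subject's status across the trial), so this extends an existing approach. The cost is SAP wording and some programming, with no new data or visits. The drawback is that unscheduled tests add some chance abnormal values to a worst-value table. A footnote can state how many entries come from unscheduled assessments.
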